### **3.2.2.2. Baseline Visit – Day 1**

The assessments and procedures to be performed on Day 1 are listed in the Schedule of Events (Table 6).

Following completion of the Day 0 assessments (ie, controlled fasting challenge and 24-hour urine collection), subjects will receive a single, peripheral IV infusion of DTX401. Safety (vital sign measurements [Section 8.2.1], clinical laboratory assessments [Section 8.2.6], and AEs and SAEs [Section 9.1]) will be monitored over 24 hours following infusion of DTX401 (Table 6). Any AEs that occur during this 24-hour observation period will be treated with appropriate supportive and medical care deemed necessary for the well-being of the subject.

Subjects will be discharged after a 24-hour observation period. Subjects in Cohort 3 will be discharged with prednisone to allow rapid treatment of possible vector-induced hepatitis if it occurs following treatment with DTX401 (Section 8.2.6.2.1). Subjects in Cohort 4 will be discharged with prednisone per the prophylactic steroid regimen (Section 8.2.6.2.2).

### **3.2.3. Follow-up Period**

Subjects will be asked to visit the study site at a minimum of every 3 to 4 days through Week 12, or longer if clinically indicated (Table 6). Following the Week 12 visit, subjects will visit the

study site approximately once every 12 weeks through Week 36 and at Week 52 or their early withdrawal from the study (Table 6).

### **3.2.3.1. Outpatient Study Site or Home Visits**

Subjects will be asked to provide clinical laboratory samples at a minimum of every 3 to 4 days through Week 12 of the study, or longer if clinically indicated (Table 6). Subjects may have the option of having these samples collected at their homes by clinically trained and qualified personnel (if arranged by the Investigator), unless there is a scheduled study site visit that the subject must attend in person (Table 6).

During these visits, a blood sample will be collected for determination of clinical chemistry (including liver function tests) and sent to the central laboratory. A second blood sample will be collected for liver function tests and sent to the local laboratory (STAT sample; Section 8.2.6.2). Saliva, urine, and stool samples will also be collected during these visits for assessment of vector shedding until at least 3 consecutive negative results are obtained from each sample matrix (Section 8.2.6.10). A blood sample will be collected for determination of cell-mediated immune response to AAV8 and G6Pase testing approximately weekly (Section 8.2.6.7).

### **3.2.3.2. Outpatient Visits**

Subjects will visit the study site on an outpatient basis at Weeks 4, 6, and 36 for efficacy and safety assessments as outlined in the Schedule of Events (Table 6).

### **3.2.3.3. Inpatient Visits**

Subjects will be admitted to the study site or hospital at Weeks 12, 24, and 52 for an [REDACTED] (Section 8.1.4), the controlled fasting challenge (Section 8.1.1), and 24-hour urine collection (Section 8.2.6.5). Each inpatient visit will last approximately 24 hours. Each subject will remain on his or her prescribed diet for the duration of each inpatient stay. The assessments and procedures to be performed at each visit are listed in the Schedule of Events (Table 6). The [REDACTED] will be performed on the day after the controlled fasting challenge to avoid having to replace the sensor prior to the fasting challenge.

A blood sample for measurement of lipid levels will be collected on the morning of hospital admission at approximately the same time as collected on Day 0. The sample should be collected at least 2 to 4 hours after the subject's last meal.

Subjects will participate in a controlled fasting challenge (Section 8.1.1). The Investigator or delegated sub-investigator will review the results of all laboratory assessments performed on the first day of the inpatient visit, including the latest cortisol values. Subjects should wear their CGM device throughout the fasting challenge, and should not change the sensor prior to the assessment. Before the controlled fasting challenge begins, the study site will provide dinner for the subject. The dinner meal will be personalized for each subject and will include a target carbohydrate range and overall composition in protein, fats and dietary fibers that is as close as possible to the subject's most current dinner dietary prescription. The content of the dinner and quantities consumed will be recorded.

After dinner, subjects will be given an oral dose of cornstarch equivalent per their most recent cornstarch prescription at approximately the same time that they typically take it, but no later than 3 hours post dinner. The time of ingestion of prefasting cornstarch and the amount consumed will be recorded. After the cornstarch is ingested, the controlled fasting challenge will begin, and the start time will be recorded accordingly. If subjects do not receive cornstarch overnight, the fasting test will begin after they complete their dinner. Subjects will be instructed to minimize activity after they finish eating dinner until the end of the fasting challenge.

During the fast, subjects may not ingest any food or drink other than water. The controlled fasting challenge will end when the subject's glucose level decreases to  $< 54$  mg/dL ( $< 3.0$  mmol/L) or when the subjects experience signs and symptoms of hypoglycemia, or when the fast reaches 15 hours without hypoglycemia, whichever occurs first. The stop time of the controlled fasting challenge will be recorded.

At the end of the controlled fasting challenge, the subject's hypoglycemia should be treated per the institution's standard procedure, which may include providing the subject with a meal, cornstarch, or IV glucose, if medically indicated.

Blood samples for measurement of cortisol, fatty acid, glucagon, insulin, C-peptide, growth hormone, IGFBP1, ACTH, alanine and ketone levels will be collected at the beginning and end of the fasting challenge, or more frequently at the Investigator's discretion. A final sample for glucose, lactate, growth hormone, IGFBP1, ACTH, and cortisol measurement will be collected 30 minutes after the end of the controlled fasting challenge. Samples should be prepared and transported to the local laboratory in accordance with the site's standard procedures. Blood samples for STAT analysis of glucose and lactate will be collected per the schedule of events. Capillary glucose will also be assessed. Urine will be collected over 24 hours (Section 8.2.6.5) for the determination of total protein, microalbumin, and creatinine. The collection of urine can overlap with the controlled fasting challenge. Subjects will be discharged following the completion of the 24-hour urine collection and the [REDACTED].

### **3.2.4. Safety Stopping Criteria**

Enrollment will be stopped and the DMC and regulators will be notified if, at any time during the study, any of the events listed below occur following administration of DTX401:

- Death of a subject
- An event with an intensity  $\geq$  Grade 3 (according to the National Cancer Institute [NCI] Common Terminology Criteria for Adverse Events [CTCAE]) develops
- Occurrence of a hepatic malignancy

If a stopping rule is met, enrollment will be paused and the DMC will meet to review available data. If a decision is made to resume enrollment, this decision will be communicated to and, if required, approved by regulatory authorities according to country requirements.

An event that meets the above criteria will be reported immediately to the Sponsor once the study site has become aware (within 24 hours). SAEs will be reported as outlined in

Section 9.1.2.2. For AEs and SAEs, the appropriate pages of the electronic case report form (eCRF) must be completed. If a stopping criterion is met and study enrollment is suspended, all subjects who have been enrolled will remain in the study and will continue to be monitored through their completion or withdrawal from the study.

### **3.2.5. End of Study**

Subjects who complete all visits up to and including the Week 52 visit (Section 3.2.3.3) will have completed the study. Subjects who discontinue before the Week 52 visit will be asked to return for an Early Withdrawal visit, during which all safety assessments should be performed (Table 6). Subjects with any ongoing AEs at this visit will continue to be monitored, as outlined in Section 9.1.5. After completion of the Week 52 visit or early withdrawal, subjects will be offered enrollment into this extension study in accordance with regulatory authority regulations and ICH GCP.

### **3.3. Changes to the Protocol due to COVID-19**

Changes to the protocol or Investigational Plan to minimize or eliminate immediate hazards or to protect the life and well-being of research participants and/or study staff may be implemented without IRB/EC approval or before filing an amendment to the competent authority but are required to be reported afterward. Investigators should contact Ultragenyx or Designee to determine an appropriate course of action, which may include but is not limited to remote visits, home health visits, and out of window visits or assessments. Any changes to the protocol or investigational plan must be documented. The Investigator will work with Ultragenyx or Designee and IRB/EC to prioritize reporting of protocol deviations that impact safety of trial participants.

## 4. SUBJECT SELECTION

Subjects will be assigned to study treatment only if they meet all of the inclusion criteria and none of the exclusion criteria.

### 4.1. Inclusion Criteria

Each subject must meet all of the following criteria at Screening to be enrolled in this study:

1. Willing and able to provide written informed consent.
2. Males and females  $\geq 18$  years of age.
3. Documented GSDIa with confirmation by molecular testing.
4. Documented history of  $\geq 1$  hypoglycemic event with glucose  $< 60$  mg/dL ( $< 3.33$  mmol/L).
5. Subject's GSDIa disease is stable as evidenced by no hospitalization for severe hypoglycemia during the 4-week period preceding the Screening Visit.
6. Hematology and coagulation panel results are within the normal range or, if outside the normal range, are deemed not clinically significant in the opinion of the Investigator.
7. No known allergic reaction to any component of DTX401.
8. Willing and able to comply with study procedures and requirements, including periodic inpatient hospitalization, frequent blood collections, and 24-hour urine collection.
9. Males and females of childbearing potential must be willing to use effective contraception at the time of administration of DTX401 and for 52 weeks following administration of DTX401 to prevent the potential transmission of the AAV vector (Section 9.2.1).

### 4.2. Exclusion Criteria

Subjects who meet any of the following criteria at Screening will be excluded from the study:

1. Screening or Baseline (Day 0) glucose level  $< 60$  mg/dL ( $< 3.33$  mmol/L); subjects may be rescreened after glucose is controlled and stable, at the discretion of the Investigator.
2. Liver transplant, including hepatocyte cell therapy/transplant.
3. Presence of liver adenoma  $> 5$  cm in size.
4. Presence of liver adenoma  $> 3$  cm and  $\leq 5$  cm in size that has a documented annual growth rate of  $\geq 0.5$  cm per year.

5. Significant hepatic inflammation or cirrhosis as evidenced by imaging or any of the following laboratory abnormalities: alanine aminotransferase (ALT) or aspartate aminotransferase > the upper limit of normal (ULN), total bilirubin > 1.5 × ULN, or alkaline phosphatase > 2.5 × ULN. Liver function tests may be repeated during the Screening Period at the Investigator's discretion.
6. Serum creatinine > 2.0 mg/dL.
7. Triglycerides ≥ 1000 mg/dL at the time of the Screening Visit.
8. Presence of active, or history of treatment for, hepatitis B virus or hepatitis C virus infection.
9. History of human immunodeficiency virus infection AND any of the following: CD4+ cell count < 350 cells/mm^3, change in antiretroviral therapy regimen within 6 months prior to Day 0, or viral load > 200 copies/mL, on 2 separate occasions, as measured by polymerase chain reaction.
10. History of a malignancy for which the subject has received treatment in the past 2 years except for prostate cancer treated with watchful waiting or surgically removed nonmelanoma skin cancer.
11. Active infection (viral or bacterial).
12. Anti-AAV8 neutralizing antibody titer ≥ 1:5.
13. Participation (current or previous) in another gene transfer study.
14. Participation in another investigational product study within 3 months of Screening.
15. Has a positive serum pregnancy test at Screening (females of childbearing potential only), a positive urine pregnancy test at Baseline (Day 0; females of childbearing potential only), or is nursing.
16. Has any other significant medical condition that the Investigator feels would be a risk to the subject or would impede the study.

## **5. SCREENING AND DOSING PROCEDURES**

### **5.1. Subject Screening**

All potential subjects must sign an informed consent form (ICF) before any study procedures or assessments are performed or initiated (Section 11.3). Subjects will have the opportunity to have any questions answered before signing the ICF. All questions raised by the subject must be addressed before the Investigator also signs the ICF. A copy of the signed ICF will be given to the subject.

Rescreening is allowed as described in Section 3.2.1. Study sites will maintain documentation of all potential subjects screened for inclusion in the study. If a subject is excluded from the study, the reasons for exclusion will be documented in the subject's source documents and on the screening log.

### **5.2. Subject Dosing**

This is an open-label study; subjects will be assigned to treatment using an interactive web response system. Three subjects will be enrolled in each cohort as described in Section 3.1.

## 6. STUDY TREATMENT

### 6.1. Identity of Study Product

#### 6.1.1. Description of DTX401

DTX401 is a nonreplicating, recombinant AAV8 vector that contains a codon-optimized, wild-type human *G6PC* coding sequence. DTX401 demonstrates thermal stability, which is a general property of AAV and parvoviruses. DTX401 is supplied as a slightly hyperosmotic buffered formulation solution of approximately 400 milliosmole at pH 8.0. DTX401 is a homogeneous, monodisperse solution that is clear and colorless without visible particulates.

#### 6.1.2. Components Used for Manufacturing

[REDACTED]

- [REDACTED]

- [REDACTED]

- [REDACTED]

[REDACTED] For additional information, please refer to the DTX401 Investigator's Brochure.

### 6.2. Management of Clinical Supplies

The study site will be provided with supplies required for infusion of DTX401.

#### 6.2.1. Packaging and Labeling

Each vial of study product provided to study sites will contain approximately 1 mL of DTX401 frozen in 2 mL sterile glass vials with a primary label on the vial. Study product will have secondary packaging with a secondary label. The primary label meets all requirements for blister and small packaging units. The secondary label will contain required text for all countries participating in the study and will include a unique identifier. Secondary labeling will appear in the appropriate language for the country supplied.

#### 6.2.2. Storage of DTX401

DTX401 must be stored in a secure freezer at a controlled temperature at or below  $-60^{\circ}\text{C}$ . The study site is to maintain a daily log documenting the temperature.

### **6.2.3. Study Product Accountability**

The Investigator or designated study site staff will maintain accurate records of receipt of all study product, including dates of receipt. In addition, accurate records will be kept regarding when and how much study product is dispensed and used by each subject in the study. Reasons for departure from the expected dispensing regimen must also be recorded. At the completion of the study, all study product will be reconciled and retained or destroyed according to instructions provided by the Sponsor.

### **6.2.4. Transmission of Infectious Agents**

Recombinant AAV vectors are nonreplicative and are not expected to pose a risk of transmission. However, all sexually active subjects must use approved contraception from the time of DTX401 dosing and for 52 weeks following administration (Section 4.1). All subjects enrolled in the study should be encouraged to discuss the use of approved contraception with his or her partner in order to prevent possible transmission of vector via seminal or vaginal fluid. The study product and post treatment study samples should be handled using standard universal precautions.

## **6.3. Treatment Schedule and Administration**

### **6.3.1. Administration of DTX401**

Subjects will receive a single peripheral IV infusion of DTX401 on Day 1, administered by qualified study personnel, as designated by the Investigator (Table 6). The dose will be determined by the cohort and candidate dose (Section 3.1).

The dose of DTX401 to be administered will be calculated using the subject's weight recorded at Screening. The subject's weight will be verified on Day 0, prior to administration of DTX401, to ensure that their current weight is within 10% of their screening weight (Section 8.2.1). Any subject weighing > 100 kg (> 220 lb) will be dosed as if his or her weight is 100 kg. Prior to infusion, all infusion bag labels will be checked by the study site pharmacist and a minimum of 2 medical personnel charged with administration of DTX401.

The study site must be equipped with emergency resuscitation capabilities. On Day 1, an IV catheter will be inserted into a peripheral vein and flushed with saline.

Detailed instructions for dose preparation and subsequent infusion of DTX401 are provided in the pharmacy manual.

### **6.3.2. Treatment Compliance**

DTX401 will be administered at the study site via a single IV infusion administered by qualified personnel. The dose, start time, stop time, and volume of infusion will be recorded in the subject's eCRF.

## **6.4. Prior and Concomitant Medications, Therapies, and Procedures**

Relevant prior and concomitant medications, therapies, and procedures will be recorded in the subject's eCRF. The minimum requirement for medications is to record the drug name, the dates of administration, and the reason for use. This includes all prescription drugs, herbal products, vitamins, minerals, and over-the-counter medications. Any changes in concomitant medication use will also be recorded in the subject's eCRF. The minimum requirement for therapies and procedures is to record the name and date of the therapy or procedure and the reason it was performed.

### **6.4.1. Permitted Medications**

The use of permitted medications (including drug name, dates of administration, dosage, reason for use) will be recorded on the appropriate page of the eCRF.

The subject will be instructed to discuss all new medications, including medications to alleviate complications associated with GSDIa and herbal supplements, with the Investigator at each study visit.

Any concomitant medication deemed necessary for the welfare of the subject during the study may be given. It is the responsibility of the Investigator to ensure that details regarding the medication are recorded in full in the eCRF.

### **6.4.2. Prohibited Medications**

Use of another investigational product is prohibited from Screening through Week 52.

## **7. WITHDRAWAL OF SUBJECTS FROM THE STUDY**

### **7.1. Study Withdrawal**

Subjects may withdraw from the study at any time and for any reason without prejudice to their future medical care by the Investigator or at the study site. Any subject who withdraws consent to participate in the study will be removed from further treatment and/or study observation immediately upon the date of request.

The Investigator must record the reason for withdrawal on the appropriate page of the eCRF. The reason for withdrawal may include the following:

- Withdrawal of consent
- Administrative decision by the Investigator or the Sponsor
- Ineligibility
- Significant protocol deviation
- Subject noncompliance
- Adverse event

If a subject is withdrawn due to an AE, the Investigator will arrange for the subject to have follow-up visits until the AE has resolved or stabilized (Section 9.1.5).

If a subject requests or decides to withdraw from the study, all efforts will be made to complete and report the observations as thoroughly as possible up to the date of withdrawal, and an early withdrawal visit will be requested.

### **7.2. Subject Replacement**

If a subject withdraws from the study after receiving DTX401, the subject will not be replaced. Subjects who withdraw from the study after signing the ICF, but before receiving DTX401, will be replaced. The replacement subject will be sequentially assigned to treatment with a new subject identification number.

## **8. STUDY ASSESSMENTS AND PROCEDURES**

### **8.1. Efficacy Assessments**

Planned time points for all efficacy measurements in the study are listed in [Table 6](#).

#### **8.1.1. Symptom-Free Euglycemia (Controlled Fasting Challenge)**

The subject's ability to maintain symptom-free euglycemia during a controlled fasting challenge will be assessed at time points specified in the Schedule of Events. However, if clinically indicated, the controlled fasting challenge can also be performed at an unscheduled visit.

The controlled fasting challenge requires a 24-hour inpatient stay in a hospital or research facility and will be performed after all other study visit assessments (except [REDACTED]) have been completed and the required laboratory assessments (as specified below) have been reviewed by the Investigator (or a subinvestigator assigned to review results and make clinical decisions per the site delegation log). Subjects should wear their CGM device throughout the fasting challenge, and should not change the sensor prior to the assessment.

If a subject is suspected to have HPA axis impairment (eg, due to prolonged steroid treatment; may be confirmed by morning cortisol or stimulation tests), the fasting challenge may have to be rescheduled to a later date in order to ensure subject safety and provide interpretable results.

Before the controlled fasting challenge begins, the study site will provide dinner for the subject. The dinner meal will be personalized for each subject, and will include a target carbohydrate range and overall composition in protein, fats and dietary fibers that is as close as possible to the subject's most current dinner prescription, but not higher in carbohydrate content than the dinner consumed at their baseline fasting challenge. The start and stop time of the dinner meal and its full dietary composition including amount of carbohydrates consumed will be recorded. After dinner, subjects will be given an oral dose of cornstarch equivalent per their most recent cornstarch prescription, at approximately the same time that they typically take it, but no later than 3 hours post dinner. The amount of cornstarch administered should not be higher than that consumed by the subject at the baseline fasting challenge. The time of ingestion of prefasting cornstarch and the amount consumed will be recorded. After the cornstarch is ingested, the controlled fasting challenge will begin, and the start time will be recorded accordingly. If a subject does not receive cornstarch before going to bed at the time of the CFC, the fasting challenge will start after they complete their dinner. Subjects will be instructed to minimize activity after they finish eating dinner until the end of the controlled fasting challenge.

During the fast, subjects may not ingest any food or drink other than water. The controlled fasting challenge will end when the subject's glucose level decreases to  $< 54$  mg/dL ( $< 3.0$  mmol/L) or when the subjects experience signs and symptoms of hypoglycemia, or when the fast reaches 15 hours without hypoglycemia, whichever occurs first. The stop time of the controlled fasting challenge will be recorded. At the end of the controlled fasting challenge, the subject's hypoglycemia should be treated per the institution's standard procedure, which may include providing the subject with a meal, cornstarch, or IV glucose, if medically indicated.

In cases where the controlled fasting challenge is terminated prematurely before the subject reaches a glucose level of < 54mg/dL or without the subject experiencing signs and symptoms of hypoglycemia, or due to any deviation in the fasting challenge protocol, an ad hoc fasting challenge may be scheduled within 6 weeks from the scheduled fasting challenge.

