### **Vaccination and Oral Prednisone Regimen**

To comply with international and regional guidelines on vaccination, as well as slight variations in regional schedules, where feasible, subjects' vaccination schedules should be adjusted to accommodate prophylactic prednisone taper regimen administration prior to and following DTX301 infusion.

Live vaccines (such as MMR and varicella) are contraindicated for patients on a substantially immunosuppressive steroid dose (ie,  $\geq 2$  weeks of daily receipt of 20 mg of prednisone, or equivalent or 1 mg/kg/day in children under 20 kg) for more than 14 days. Thus, Investigators should time administration of live vaccines to at least 14 days prior to inception of the prednisone regimen, or after completion of the 8-week prednisone regimen.

Inactivated vaccines and seasonal influenza prophylaxis vaccination are not precluded to patients treated with immunosuppressive agents in accordance to international guidelines ([Ezeanolue et al.; Rubin et al., 2014; Public Health England, 2020; ECDC, 2017; Public Health England, 2017](#)). All inactivated vaccines can be administered safely to persons with altered immunocompetence, whether the vaccine is a killed whole-organism or a recombinant, subunit, split-virus, toxoid, polysaccharide, or polysaccharide protein-conjugate vaccine.

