5.1. Baseline

Baseline is defined as the last non-missing assessment taken prior to the dose of DTX401, unless specified otherwise.

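### The six-week repeat rule for an invalid fasting challenge does not say how it applies at Day 0 or Week 52, and by default the SAP keeps an invalid Day 0 time as the baseline

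*Protocol*

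**What the plan says.** Protocol 8.1.1 deals with a challenge stopped before low glucose or symptoms, or run with a deviation: "an ad hoc fasting challenge may be scheduled within 6 weeks from the scheduled fasting challenge". No visit is named and none is excepted. By contrast, note dd to the Schedule of Events, on a Week 12 challenge put off because of steroids, gives the visit, a limit of 8 weeks and the visit type.

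On timing, Protocol 6.3.1 states "Subjects will receive a single peripheral IV infusion of DTX401 on Day 1", and 3.2.2.2 gives the order: "Following completion of the Day 0 assessments (ie, controlled fasting challenge and 24-hour urine collection), subjects will receive a single, peripheral IV infusion of DTX401". Neither section defines what completing the challenge means. Protocol 3.2.5 treats as finished with the study those "Subjects who complete all visits up to and including the Week 52 visit". The length of the Cohort 4 steroid course appears in the vaccination text, which places live vaccines before the course or "after completion of the 8-week prednisone regimen".

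SAP 5.1 reads: "Baseline is defined as the last non-missing assessment taken prior to the dose of DTX401, unless specified otherwise". SAP 8.5.1 places the baseline challenge on Day 0. It takes the termination time as the event time when the challenge stops for symptoms or when an intervention is given, and uses 15 h when there is no hypoglycemic event. It has no category for an invalid challenge. SAP 8.1 tabulates by scheduled visit, without windows unless stated otherwise. SAP 8.5.2 does state otherwise for cornstarch data, with a window and a fallback to unscheduled visits. SAP 8.5.1 has nothing comparable for the fasting challenge.

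**The concern.** The only secondary endpoint is the change from baseline in fasting time at Weeks 12, 24 and 52. A bad baseline therefore enters all three changes for that subject, in cohorts of 3. The protocol foresees challenges that fail and offers a repeat, but at the visit where a failure matters most the repeat, as scheduled, comes after the gene transfer. The SAP then has no step that recognises the Day 0 value as invalid, and its two scoring rules push the result in opposite directions depending on why the fast was stopped. A repeat that is done at a later visit also has no assigned place in the analysis.

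**Working it through.** 1. **Plan's own figure.** Protocol 3.2 gives about 60 weeks per subject. Screening of 56 days is 56/7 = 8 weeks, and 8 + 52 = 60. The figure reproduces and contains no time for a repeat after Week 52.

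2. **Day 0.** Six weeks is 42 days, so a repeat could fall on Days 1 to 42. The challenge starts after dinner, so the earliest repeat is the evening of Day 1. With the infusion on Day 1, 0 of the 42 days precede it. In Cohort 4 prednisone starts on Day 1 and runs 8 × 7 = 56 days as planned, so all 42 days also lie within it. Protocol 10.2.3.1 lists challenges only at Day 0 and Weeks 12, 24 and 52, so the Day 0 value is the only scheduled one that SAP 5.1 can select.

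3. **Week 52.** Take Week 52 as Day 364, with the ±7-day window as I read the Schedule of Events (Days 357 to 371).

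| Challenge on | Repeat limit | Repeat days inside window | Repeat days after window |
|---|---|---|---|
| Day 357 | Day 399 (Week 57) | 14 | 28 |
| Day 364 | Day 406 (Week 58) | 7 | 35 |
| Day 371 | Day 413 (Week 59) | 0 | 42 |

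For comparison, the limits for the other visits are 84 + 42 = Day 126 (Week 18) and 168 + 42 = Day 210 (Week 30), both well inside the study.

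4. **Effect of one invalid baseline.** Assumptions, not document figures: the true fasting time is 300 to 420 min and the fast is stopped at 120 min. The shift in a 3-subject mean change is (true − recorded)/3.
   - Intervention given, so 120 min is recorded: (300 − 120)/3 = +60 min; (420 − 120)/3 = +100 min.
   - No event and no intervention, so a literal reading of SAP 8.5.1 records 15 h = 900 min: (300 − 900)/3 = -200 min; (420 − 900)/3 = -160 min. Because 900 min is the maximum, that subject's change can never be positive.

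5. **Chance of at least one among the 3 Cohort 4 baselines.** The documents give no invalid rate; assume 5% to 10%. Then 1 − 0.95³ = 0.143 and 1 − 0.90³ = 0.271, or 14% to 27%.

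**The case against.** The best reply is that the protocol is silent on these cases and does not block a remedy. The repeat rule is permissive, and six weeks is an upper limit. The infusion follows completion of the Day 0 challenge, and a challenge ended prematurely is arguably not complete. Nothing forbids holding the infusion or re-setting Day 0, and SAP 5.1 would pick up a repeat done before dosing. At Week 52 a repeat can fit inside the window unless the challenge was on its last day, and 3.2.5 does not say that an invalid challenge completes the visit. Section 8.1.1 also allows unscheduled challenges when clinically indicated.

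Much of this stands. A reader might infer that an invalid baseline or Week 52 challenge can never be recovered; the documents do not show that. But they give no instruction to recover it either. The provisions for postponing a challenge over cortisol or adrenal concerns act before it starts, not after it fails. Re-setting Day 0 is limited by the 56-day screening period (42 days left if 14 are used, 14 if 42 are used), and note cc requires the dosing visit to be booked at least 3 days ahead.

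Three other stronger readings also fail:
- **All 12 baselines are at risk under this rule**, a 46% to 72% chance of at least one invalid (1 − 0.95¹² and 1 − 0.90¹²). Protocol 1.3.1 already reports Week 52 challenges from Cohorts 2 and 3, and Cohort 1 was dosed before them. At Day 0 the present text can reach only Cohort 4.
- **The error always flatters the treatment.** It does so only in the intervention case; the 15 h rule works the other way.
- **Every invalid baseline distorts the later test meals**, because 8.1.1 caps follow-up dinner carbohydrate and cornstarch at baseline intake. Both are consumed before the fast, so stopping early changes neither. Only a meal or cornstarch deviation carries forward.

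**Conclusion.** The point holds as a gap between the protocol's repeat rule, its dosing schedule and the SAP's scoring rules. On the written schedule a Day 0 repeat is post-treatment, most or all of the Week 52 repeat period lies after study completion, and an invalid Day 0 value becomes the baseline unless someone takes a step that the documents do not describe. The SAP also gives no rule for using a repeat at Week 12 or 24, where the timing does work.

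The shifts of +60 to +100 min and -160 to -200 min rest on the assumed stop at 2 h, the assumed true time and, for the second range, a literal reading of SAP 8.5.1. The 14% to 27% rests on the assumed invalid rate. SAP 3.7 records that the data monitoring committee had already reviewed Cohort 4 through Week 24, so the SAP rules and the Week 52 wording are where a change helps most.

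**What to change.** In SAP 5.1 and 8.5.1:
- Define a valid challenge as one ended by glucose below the threshold, by symptoms or at 15 h, without a deviation that affects the fasting time.
- Apply the 15 h value only to fasts that actually reached 15 h.
- Use a valid ad hoc repeat in place of an invalid Week 12, 24 or 52 challenge, as a stated exception to the scheduled-visit rule in 8.1.
- Show a subject without a valid pre-dose challenge with absolute times only, leave that subject out of change from baseline, and state n at each visit.

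In the protocol, reconcile 8.1.1 with 3.2.2.2 and 3.2.5: say how the repeat rule applies at Day 0, what completion of the Day 0 challenge means, and whether a Week 52 repeat outside the visit window belongs to this study. The dosing sequence is for the sponsor to decide. If Week 52 repeats are allowed to the full limit, time in study becomes 8 + 52 + 6 = 66 weeks, or 67 if the challenge is on the last day of the window, against the stated 60.

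The cost is a few sentences and an occasional smaller n for change from baseline.
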